9.7.3 Interim Analysis

In order to make decisions about the remainder of the study as well as the full E2609 clinical development program, the sponsor will unblind safety, PK, and PD data on an ongoing basis and perform interim analyses of these data. Investigators, other clinical site staff, subjects and caregivers/informants will remain blinded to study treatment. (revised per Amendment 03)

An interim safety analysis will also be conducted when the Stage A subjects have completed 12 weeks of treatment (or discontinue study drug early) in Stage A. (revised per Amendments 01, 03, and 04)

The MCI/Prodromal Cohort

The Bayesian interim analyses and response adaptive randomization will be conducted by an unblinded external independent analysis group in accordance with the protocol. Oversight of the Bayesian interim analyses and response adaptive randomization will be conducted by an independent unblinded committee that has expertise with Bayesian adaptive design in clinical studies to ensure that the response adaptive randomization process and interim analyses

perform as expected. The analysis group will provide the interim analysis outcomes to the committee at each interim analysis. The committee will ensure the integrity of the interim analysis and response adaptive randomization process through review of efficacy data. In addition, the committee will act in an independent advisory capacity to monitor the Bayesian interim analysis outcomes according to the early success and futility boundaries prespecified in the protocol. The committee will not be charged with any subject safety issues; this will remain the responsibility of the DSMB.

If the predefined early success criteria are met during the recruitment period, further recruitment and enrollment of MCI/Prodromal subjects into the study will stop (following confirmation from the Sponsor's Senior Management) and all currently randomized subjects will complete the full 18 months of treatment. No further interim analyses will be conducted after achieving early success.

If the predefined threshold for futility is reached, no additional subjects will be randomized into the study and the treatment of subjects already randomized into the study will stop and the study will be declared as "failed". All subjects will be monitored for safety for 3 months following their last dose.

If neither early success nor futility is reached and the study reaches full randomization, all subjects will complete 18 months of treatment. Interim efficacy analyses will be conducted every 3 months after full randomization is reached to assess futility and early success until all subjects complete 18 months of treatment. After full randomization, all study subjects will stop treatment only in the event of futility.

The DSMB will continue to monitor the safety aspects of the study throughout Stage A and Stage B. Details will be provided in the DSMB Charter. The study may be stopped for safety at any time.

The first Bayesian adaptive interim analysis will be conducted when 100 MCI/Prodromal subjects have been randomized into the study (ie, including MCI/Prodromal subjects from Stage A and Stage B). (revised per Amendment 01) Further interim efficacy analyses will be conducted after each additional 50 MCI/Prodromal subjects have been randomized, to a maximum of 500 MCI/Prodromal subjects (ie, at 100, 150, 200, 250, 300, 350, 400, 450, and 500 subjects randomized). If the study reaches full randomization, additional interim analyses will be conducted every 3 months until all subjects complete 18 months of treatment. The study will be monitored for futility at each interim analysis. Starting at the interim analysis for 200 subjects, the study will be monitored for success at each interim analysis. Each interim analysis will be conducted on data for the derived ADCOMS.

In addition, at each interim efficacy analysis, response adaptive randomization will be used to update the allocation of new subjects between placebo and active doses according to a predefined automated algorithm.

The Mild to Moderate AD Cohort (revised per Amendment 01)

A group sequential design will be used for the Mild to Moderate AD cohort. (revised per Amendment 01) This design includes 3 looks, 2 interim looks (when 60% and 80% information fractions are achieved) and 1 final look. The information fraction is the number of assessments in all treatment arms divided by the total number of expected assessments. Interim analyses will be performed after the MCI/Prodromal cohort crosses the early success boundary. The corresponding efficacy boundaries will be 0.076, 0.022, and 0.0423 for the first, second, and final analyses, respectively. If the actual information fraction during the interim analyses is different from 60% or 80% at the interim, the efficacy boundaries will be adjusted based on the actual information fraction.

If early success in the MCI/Prodromal cohort is not achieved before the final analysis that is performed when all subjects have completed 18 months treatment, then only a final analysis will be performed in mild to moderate AD subjects. In the event of futility in the MCI/Prodromal cohort, an analysis will be performed for the Mild to Moderate AD cohort based on the data for mild to moderate AD subjects available at that time. (revised per Amendment 01)

Randomization into the Mild to Moderate AD cohort will remain at a fixed schedule throughout Stage B. (revised per Amendment 01)

The interim analyses in the Mild to Moderate AD cohort will be conducted by an independent analysis group. (revised per Amendment 01)

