9.7.1.1.2 SECONDARY ENDPOINTS

Change from baseline in: (revised per Amendment 02)

- Total hippocampal atrophy at 12 and 18 months of treatment in MCI/Prodromal subjects as measured by vMRI
- The derived ADCOMS at 18 months of treatment in mild to moderate AD subjects (revised per Amendment 01)

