All mild to moderate AD subjects will be included in the efficacy evaluations of the Mild to Moderate AD cohort. The analysis of the Mild to Moderate AD cohort is based on the group sequential design. Interim analyses in the Mild to Moderate AD cohort will only be performed after the MCI/Prodromal cohort crosses the early success boundary. The early efficacy signal based on the change from baseline of ADCOMS at 18 months is defined as crossing the interim-analysis boundaries for overwhelming efficacy in the mild to moderate AD population. The O'Brien-Fleming (OF) boundaries based on Lan-DeMets alpha spending function will be used to assess overwhelming efficacy. The corresponding OF boundaries based on *P* values will be 0.076, 0.0221, and 0.0423 for the first, second, and final analyses, respectively, according to 2 planned interim analyses at the 60% and 80% information fraction. (revised per Amendment 01)

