The null and alternative hypotheses and the statistical test are the same as those for vMRI. To estimate the sample size for the amyloid PET imaging subgroup at 18 months, a common SD of the change from baseline was estimated at 0.33 and a reasonable mean difference between treatment and placebo was estimated as 0.25 (standardized uptake value ratio [SUVR]). Assuming a moderate dose-response, the best dose would achieve a difference of 0.25 (SUVR) and the middle and low doses would achieve a difference of 0.2 and 0.15 (SUVR), respectively; this would require a total of 100 subjects from all 4 arms at 18 months to achieve 80% power.

9.7.2.2 Sample Size Rationale for the Mild to Moderate AD Cohort (revised per Amendment 01)

ADCOMS at Month 18

The null hypothesis is that there is no difference between active dose and placebo. There are 2 null hypotheses corresponding to 2 active doses. The alternative hypothesis is that at least 1 null hypothesis is false. The null hypotheses will be tested using Dunnett's test with 2-sided alpha of 0.05 as described for the Mild to Moderate AD cohort in [Section 9.7.1.6.2](#). The statistical power was estimated through simulation for the dose-response assumption that the percent reduction in change from baseline of ADCOMS at 18 months compared with placebo would be 33% and 50% corresponding to the 2 doses, respectively. The estimated power for the actual planned 200 mild to moderate AD subjects is approximately 80% assuming a 2-sided alpha of 0.05. (revised per Amendment 01)

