9.7.4 Other Statistical/Analytical Issues

Adaptive Randomization in the MCI/Prodromal Cohort

Randomization to placebo or 1 of 3 dose groups of E2609 will be fixed for the first 100 MCI/Prodromal subjects randomized in the study (1:1:1:1; placebo to each of the 3 active doses for the first 100 MCI/Prodromal subjects randomized, including those randomized from both Stage A and Stage B). Thereafter, randomization probabilities to each treatment group will be updated at each interim analysis, such that the randomization probability will be increased for the placebo group and dosage groups that represent the potential target dose (ED₉₀), and simultaneously decreased for other active arms. (revised per Amendment 01)

Randomization in the Mild to Moderate AD Cohort (revised per Amendment 01)

In Stage A, the mild to moderate AD subjects will be randomized to placebo or 1 of 3 E2609 dose groups (5, 15, and 50 mg of E2609) at a 1:1:1:1 ratio, while in Stage B, the mild to moderate AD subjects will be randomized to placebo or 1 of 2 E2609 dose groups (15 and 50 mg E2609) at a 1:1:1 ratio. (revised per Amendment 01)

Stratification (revised per Amendment 01)

Within the 2 clinical cohorts (MCI/Prodromal and mild to moderate AD), subjects will be stratified at randomization by *ApoE4* status (positive or negative) and prior treatment with AChEIs or memantine or both (yes or no). (revised per Amendment 01)

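### The AD-cohort information fraction is a count of assessments that is not tied to Month-18 ADCOMS in the tested arms; if all visits count, the looks can come early and two-sided alpha can drift from 5%

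*Protocol*

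**What the plan says.** Section 9.7.3 gives the AD cohort a group sequential design with "2 interim looks (when 60% and 80% information fractions are achieved) and 1 final look". It then defines the scale on which those looks are placed: "The information fraction is the number of assessments in all treatment arms divided by the total number of expected assessments". If the achieved fraction differs from 60% or 80%, the boundaries are to be recomputed at the achieved fraction, which is measured by the same definition. The looks take place only after the MCI/Prodromal cohort has crossed its early success boundary.

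Section 9.7.1.6 says that O'Brien-Fleming "boundaries based on Lan-DeMets alpha spending function will be used to assess overwhelming efficacy", with nominal p-values "0.076, 0.0221, and 0.0423 for the first, second, and final analyses, respectively". Section 9.7.3 repeats them with the second rounded to 0.022.

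The tested quantity is narrower than a count of assessments. Section 9.7.1.1.2 lists the endpoint as "The derived ADCOMS at 18 months of treatment in mild to moderate AD subjects". Section 9.7.2.2 describes two null hypotheses, one per active dose, under a Dunnett "test with 2-sided alpha of 0.05 as described for the Mild to Moderate AD cohort". Section 9.7.1.6.2 analyses the endpoint by MMRM. Section 9.7.4 adds an arm outside those two contrasts: "In Stage A, the mild to moderate AD subjects will be randomized to placebo or 1 of 3 E2609 dose groups", the third dose being 5 mg.

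**The concern.** In a spending-function design the information fraction must measure information about the tested parameter, because it sets both how much alpha is released at each look and the correlation assumed between looks. Here the parameter is the Month-18 contrast, while the stated measure is a number of assessments. The ADCOMS components are collected at Visits 11, 14, 15, 16, 17 and 18 (nominal months 3, 6, 9, 12, 15 and 18), and the early visits accrue first. A count over all visits therefore runs ahead of the count of Month-18 values.

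Two things follow on that reading. The spending function releases alpha for Month-18 data not yet collected, and the looks are less correlated than the boundaries assume. A stop for overwhelming efficacy could also rest on a small share of the 18-month data. Adjusting to the actual fraction is no protection, because that fraction comes from the same count.

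**Working it through.** **Inputs from the protocol.** Looks at 0.60, 0.80 and 1.00; Lan-DeMets O'Brien-Fleming spending; two-sided alpha 0.05; up to 200 AD subjects including those from Stage A (Section 9.3); six post-baseline treatment visits; MMRM analysis.

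**Assumptions, not in the protocol.** Uniform accrual over R = 12 to 36 months, no dropout, and a single comparison (Dunnett correlation ignored). For the MMRM check, within-subject correlation 0.5 to 0.85, either AR(1) or compound symmetry.

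**1. The plan's own boundaries.** Spending 0.025 on each side gives cumulative two-sided alpha 4[1 − Φ(2.2414/√t)]: 0.0076 at t = 0.6, 0.0244 at 0.8 and 0.0500 at 1. Solving recursively gives z = 2.669, 2.289, 2.031, or p = 0.0076, 0.0221, 0.0423. The second and third match the protocol. The first is printed as 0.076, ten times too large; as printed, overall alpha is 9.7% even when the fractions are exactly right. That is a separate error. The steps below use 0.0076 so as to isolate the effect of the fraction. At true fractions 0.6/0.8/1.0 these boundaries give 5.0%.

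**2. When an all-visits count reaches 60% and 80%.** The share of subjects past visit v at calendar month T is min(1, max(0, (T − v)/R)), and the counted fraction is the mean over the six visits. For R = 24:

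- At T = 24.9 the shares are 0.9125, 0.7875, 0.6625, 0.5375, 0.4125 and 0.2875. Their sum is 3.6, and 3.6/6 = 0.60. The Month-18 share is 29%, at most 0.2875 × 200 ≈ 58 subjects.
- At T = 30.3 the shares are 1, 1, 0.8875, 0.7625, 0.6375 and 0.5125. Their sum is 4.8, and 4.8/6 = 0.80. The Month-18 share is 51%.

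**3. Overall alpha at the true Month-18 fractions**, completers only, boundaries 0.0076/0.0221/0.0423:

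| Accrual (months) | Month-18 share at the 60% look | Month-18 share at the 80% look | Two-sided alpha |
|---|---|---|---|
| 12 | 2.5% | 35% | 6.5% |
| 18 | 19% | 45% | 6.1% |
| 24 | 29% | 51% | 5.9% |
| 30 | 35% | 56% | 5.7% |
| 36 | 39% | 59% | 5.6% |

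The ceiling with independent looks is 7.1%. Table 7 also schedules the same scales at follow-up Visits 19 and 20 (months 19 and 21). If those are counted too, the Month-18 shares are 28% to 46% and 62% to 67%, and alpha is 5.4% to 5.7%.

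**4. Allowing for MMRM.** Earlier visits carry some Month-18 information. Take the true fraction as the inverse variance of the Month-18 mean at the look divided by its value at the end. Selected results:

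| Structure, correlation | Accrual (months) | True fractions | Alpha |
|---|---|---|---|
| AR(1), 0.5 | 12 | 0.03, 0.40 | 6.4% |
| AR(1), 0.7 | 24 | 0.36, 0.60 | 5.7% |
| Compound symmetry, 0.7 | 24 | 0.50, 0.74 | 5.2% |
| Compound symmetry, 0.85 | 18 | 0.55, 0.82 | 5.0% |
| Compound symmetry, 0.85 | 36 | 0.67, 0.88 | 4.7% |

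Over the whole grid alpha runs from 4.7% to 6.4%.

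**5. The 5 mg subjects alone.** If n5 of the 200 are on 5 mg and all their data are in, the tested-arm fraction at a counted q is (200q − n5)/(200 − n5). With 30 Stage A AD subjects, n5 = 7.5: (120 − 7.5)/192.5 = 58% and (160 − 7.5)/192.5 = 79%. With 72 (the Stage A maximum, 60 + 20%), n5 = 18: 102/182 = 56% and 142/182 = 78%. Alpha is 5.03% to 5.09%.

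**6. What the boundaries would be on the right scale.** If the looks truly fall at 28.7% and 51.3% of Month-18 data (completers only), the same spending function gives nominal p-values of about 0.00006, 0.0035 and 0.0489.

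**The case against.** The strongest reply is that the sentence does not say assessments at all visits. Section 9.7.1.6 ties the interim signal to ADCOMS at 18 months, so a Month-18 count is a possible reading, and on it the early-look mechanism disappears. This stands: a reader might infer that the protocol prescribes an all-visits count, and it does not. But it does not prescribe a Month-18 count either, and a rule whose first look could fall at 60% or at about 29% of Month-18 data is badly fixed. Nor is this simply detail deferred to the SAP, because the protocol itself states the definition and attaches the boundary adjustment to it.

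A reader might also infer that alpha must exceed 5%. The documents do not support that. Under MMRM with high compound-symmetric correlation and accrual of 18 months or more, alpha is 4.7% to 5.0%, and neither correlation nor accrual is given. Uniform accrual also ignores the planned recruitment pause after Stage A, and nothing in the protocol supports the 12-month case that supplies the extremes.

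The gate matters as well. AD looks require MCI/Prodromal early success. If the drug does nothing in either cohort, Section 9.7.2.1 puts false success at no more than 5%, so the added error is at most about 0.05 × 1.5 = 0.08 point. The alpha figures above apply once the gate has opened, chiefly when the drug works in MCI/Prodromal but not in AD. On the other hand, the gate makes looks away from 60% and 80% more likely, so the boundaries are more likely to be recomputed from this count.

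Finally, the endpoint is secondary in a Phase 2 study, and the printed 0.076 is the larger error. Both are true, but correcting the misprint leaves this definition as it is.

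**Conclusion.** The concern holds as a defect of definition. The information fraction is not tied to the tested quantity, and the adjustment rule inherits the same count. On an all-visits reading the nominal 60% and 80% looks can come well before that share of Month-18 data exists. Conditional on the gate having opened, on the corrected first boundary and on assumed uniform accrual of 12 to 36 months without dropout, two-sided alpha is about 5.6% to 6.5% counting completers and about 4.7% to 6.4% with MMRM information. The protocol shows neither that the looks will be early nor that alpha will exceed 5%; both depend on the reading chosen and on quantities it does not give. The part due to 5 mg subjects is under 0.1 point. This should be fixed, but the likely effect is modest.

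**What to change.** Replace the definition in Section 9.7.3 with one tied to the test. The information fraction would be the information on the Month-18 ADCOMS contrast in the placebo, 15 mg and 50 mg AD arms, measured as the ratio of the inverse variance of that contrast at the look to its planned final value. A simpler alternative is the number of Month-18 ADCOMS assessments observed in those three arms divided by the number planned there. Compute the spending boundaries, and any adjustment at an interim, from that fraction. The inverse-variance form credits the earlier visits that the MMRM uses; the count does not.

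The change costs one sentence in the protocol, repeated in the SAP, before any AD look. The interim looks may come somewhat later. Correct the first boundary in the same edit, since the stated spending function gives 0.0076 and not 0.076.

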9.7.4 Other Statistical/Analytical Issues

Adaptive Randomization in the MCI/Prodromal Cohort

Randomization to placebo or 1 of 3 dose groups of E2609 will be fixed for the first 100 MCI/Prodromal subjects randomized in the study (1:1:1:1; placebo to each of the 3 active doses for the first 100 MCI/Prodromal subjects randomized, including those randomized from both Stage A and Stage B). Thereafter, randomization probabilities to each treatment group will be updated at each interim analysis, such that the randomization probability will be increased for the placebo group and dosage groups that represent the potential target dose (ED₉₀), and simultaneously decreased for other active arms. (revised per Amendment 01)

Randomization in the Mild to Moderate AD Cohort (revised per Amendment 01)

In Stage A, the mild to moderate AD subjects will be randomized to placebo or 1 of 3 E2609 dose groups (5, 15, and 50 mg of E2609) at a 1:1:1:1 ratio, while in Stage B, the mild to moderate AD subjects will be randomized to placebo or 1 of 2 E2609 dose groups (15 and 50 mg E2609) at a 1:1:1 ratio. (revised per Amendment 01)

Stratification (revised per Amendment 01)

Within the 2 clinical cohorts (MCI/Prodromal and mild to moderate AD), subjects will be stratified at randomization by *ApoE4* status (positive or negative) and prior treatment with AChEIs or memantine or both (yes or no). (revised per Amendment 01)

9.7.5 Procedure for Revising the Statistical Analysis Plan

If the statistical analysis plan needs to be revised after the study starts, the sponsor will determine how the revision impacts the study and how the revision should be implemented. The details of the revision will be documented and described in the clinical study report.

11 PROCEDURES AND INSTRUCTIONS (ADMINISTRATIVE PROCEDURES)

11.1 Changes to the Protocol

Any change to the protocol requires a written protocol amendment or administrative change that must be approved by the sponsor before implementation. Amendments specifically affecting the safety of subjects, the scope of the investigation, or the scientific quality of the study require submission to health or regulatory authorities as well as additional approval by the applicable IRBs/IECs. These requirements should in no way prevent any immediate action from being taken by the investigator, or by the sponsor, in the interest of preserving the safety of all subjects included in the study. If the investigator determines that an immediate change to or deviation from the protocol is necessary for safety reasons to eliminate an immediate hazard to the subjects, the sponsor's medical monitor and the IRB/IEC for the site must be notified immediately. The sponsor must notify the health or regulatory authority as required per local regulations.

Protocol amendments that affect only administrative aspects of the study may not require submission to health or regulatory authority or the IRB/IEC, but the health or regulatory authority and IRB/IEC (or if regionally required the head of the medical institution) should be kept informed of such changes as required by local regulations. In these cases, the sponsor may be required to send a letter to the IRB/IEC and the Competent Authorities (or, if regionally required, the head of the medical institution) detailing such changes.

11.2 Adherence to the Protocol

The investigator will conduct the study in strict accordance with the protocol (refer to ICH E6, Section 4.5).

11.3 Monitoring Procedures

The sponsor's or CRO's CRA will maintain contact with the investigator and designated staff by telephone, letter, or email between study visits. Monitoring visits to each site, and potential remote source document verification, will be conducted by the assigned CRA as described in the monitoring plan. The investigator (or if regionally required, the head of the medical institution) will allow the CRA to inspect the clinical, laboratory, and pharmacy facilities to assure compliance with GCP and local regulatory requirements. The eCRFs and subject's corresponding original medical records (source documents) are to be fully available for review by the sponsor's representatives at regular intervals. These reviews verify adherence to study protocol and data accuracy in accordance with local regulations. All records at the site are subject to inspection by the local auditing agency and to IRB/IEC review.

In accordance with ICH E6, Section 1.52, source documents include, but are not limited to, the following:

- Clinic, office, or hospital charts
- Copies or transcribed health care provider notes that have been certified for accuracy after production
- Recorded data from automated instruments such as IxRS, x-rays, and other imaging reports (eg, sonograms, computed tomography scans, MRIs, radioactive images, ECGs, rhythm strips, electroencephalography, polysomnographs, pulmonary function tests) regardless of how these images are stored, including microfiche and photographic negatives
- Pain, quality of life, or medical history questionnaires completed by subjects
- Records of telephone contacts
- Diaries or evaluation checklists
- Drug distribution and accountability logs maintained in pharmacies or by research personnel
- Laboratory results and other laboratory test outputs (eg, urine pregnancy test result documentation and urine dip-sticks)
- Correspondence regarding a study subject's treatment between physicians or memoranda sent to the IRBs/IECs
- CRF components (eg, questionnaires) that are completed directly by subjects and serve as their own source

